9.6.8 Adverse Events

Adverse events (Section 14.1) will be recorded by the Investigator from the time the subject signs informed consent to 28 days after the last dose of IP. The AEs, including SAEs, will be recorded on the AE page of the eCRF and in the subject's source documents. All SAEs must be reported to PPM SERVICES SA Drug Safety within 24 hours of the Investigator's knowledge of the event (see Section 14.5). Worsening of a subject's UC, including UC flare, should be considered as worsening of disease under study, and should not be captured as an AE. Worsening or exacerbation of UC, including UC flare, meeting the definition of an SAE should be reported as an SAE.

9.7 Efficacy Assessments

9.7.1 Subject Diary for Ulcerative Colitis Disease Activity

Subjects will be provided with the Subject Diary for UC Disease Activity at study visits in order to record the following information:

(1) Frequency of bowel movements:

As usual
1-2 times a day more than usual
3-4 times a day more than usual
More than 5 times a day more than usual

(2) Blood in stools

Absent Traces of blood in stools A lot of blood in stools Blood only

(3) General Well-Being

Generally Well Fair Poor Terrible

Diaries will be completed throughout the study and assessed at the clinic, at each study visit, from screening until the Week 8 Visit or Early Termination Visit. The information extracted will be used for calculation of the Mayo score. In order to encourage consistent diary recording, subjects are required to enter diary data continuously throughout the study. The method of diary data collection will be electronic data capture and may include paper.

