22 APPENDICES

Appendix A Subject Diary for Ulcerative Colitis Disease Activity

Based on Ulcerative Colitis Disease Activity Index (Schroeder 1987)

Please tick the appropriate box		
(1)Frequency of bowel movements: As usual 1-2 times a day more than usual 3-4 times a day more than usual More than 5 times a day more than usual		0000
(2)Blood in stools Absent Traces of blood in stools A lot of blood in stools Blood only		0000
(3)General Well-Being Generally Well Fair Poor Terrible		0000

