Appendix C Modified Mayo Scoring System

Stool Frequency Sub-score (SFS)*

- 0 = Normal number of stools for this patient
- 1 = 1 2 stools more than normal
- 2 = 3 4 stools more than normal
- 3 = 5 or more stools more than normal
- * Each patient serves as his or her own control to establish normal stool frequency and the degree of abnormal stool frequency.

Rectal Bleeding Sub-score (RBS)**

- 0 = No blood seen
- 1 = Streaks of blood with stool less than half the time
- 2 = Obvious blood with stool most of the time
- 3 = Blood alone passed
- ** The daily bleeding score represents the most severe bleeding of the day.

Endoscopy sub-score: Findings of flexible sigmoidoscopy

- 0 = Normal or inactive disease
- 1 = Mild disease (erythema, decreased vascular pattern)
- 2 = Moderate disease (marked erythema, absent vascular pattern, friability, erosions)
- 3 = Severe disease (spontaneous bleeding, ulceration)

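### The diary has no box for exactly 5 extra stools, although the Mayo scale gives that count the top stool score; the mapping from the bleeding boxes to RBS 1 and 2 is also not stated

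*Combined protocol and SAP*

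**What the plan says.** Section 9.7.1 describes a daily diary whose entries are used to calculate the Mayo score, and Appendix A prints the same categories. For stool frequency the third box is "3-4 times a day more than usual" and the fourth is "More than 5 times a day more than usual". Appendices B and C put 3 to 4 extra stools at SFS 2 and define SFS 3 as "5 or more stools more than normal".

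For bleeding, the diary offers four grades by amount, the second being "Traces of blood in stools" and the third a lot of blood. Appendix C defines RBS 1 as "Streaks of blood with stool less than half the time" and RBS 2 as obvious blood for most of the time. A footnote makes the daily score the worst bleeding of that day.

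Section 13.6 says that the subject rates both items. The investigator then averages the last 3 available days within the 5 days before each visit. The document gives neither a diary-to-sub-score conversion nor a rounding rule for the average.

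**The concern.** Two of the three MMS components come from this diary; the third is the endoscopy read. If the boxes do not line up with the scale, the same day can receive different scores from different subjects, and nothing in the document says how to resolve it.

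The gap sits between SFS 2 and SFS 3, where many active subjects may lie at baseline. It therefore bears on baseline MMS, on change in MMS (Section 7.3) and on clinical response, which needs a fall of at least 2 points and 25% together with an RBS condition (Section 7.2.1). The bleeding boxes raise a related question at the boundary between RBS 1 and 2, which the secondary endpoint of RBS 1 or less at Week 8 uses directly.

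**Working it through.** The plan gives no figure for this point, so there is none to reproduce; the sample size of 69 per group is not in dispute. I assume that the four boxes are scored 0 to 3 in order and that the Section 13.6 averaging also forms the baseline score.

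**1. Stool boxes against the scale**

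| Extra stools in the day | Diary box (9.7.1, App. A) | SFS (App. B, C) |
|---|---|---|
| 0 | first | 0 |
| 1 to 2 | second | 1 |
| 3 to 4 | third | 2 |
| exactly 5 | none | 3 |
| 6 or more | fourth | 3 |

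A subject with 5 extra stools may tick the third box (scored 2, one too low) or the fourth (scored 3, correct).

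**2. Effect on the visit score**

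Visit SFS = (d1 + d2 + d3)/3. If k of the three days had exactly 5 extra stools and were ticked in the third box, the average falls by k/3: 0.33, 0.67 or 1.00 for k = 1, 2, 3.

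**3. Clinical response**

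Take a subject exactly on the threshold, with 5 extra stools on all three baseline days.

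- True baseline: SFS 3 + RBS 2 + endoscopy 2 = 7.
- Week 8: 2 + 1 + 2 = 5. The fall is 2 points, 2/7 = 28.6%, with RBS down by 1: a response.
- k = 1: baseline 6.67, fall 1.67.
- k = 2: baseline 6.33, fall 1.33.
- k = 3: baseline 6, fall 1 (1/6 = 16.7%).

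With unrounded averages the response is lost from k = 1. With SFS rounded to the nearest whole number it is lost from k = 2, because 2.33 becomes 2 while 2.67 stays at 3. A subject with a true fall from 8 to 5 would still respond even at k = 3 (7 to 5, 28.6%). The error also runs the other way: a Week 8 day of exactly 5 ticked too low makes improvement look larger.

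**4. Remission cut (SFS of 1 or less)**

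SFS 2 and SFS 3 both fail the cut, so a uniform set of days cannot change remission. Mixed days can:

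- Unrounded: days (0,1,3) average 4/3 = 1.33; recorded as (0,1,2) they average 1.00.
- Rounded to nearest: days (1,1,3) average 5/3 = 1.67, which becomes 2; recorded as (1,1,2) they average 1.33, which becomes 1. Days (0,2,3) behave the same way.

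The patterns that matter therefore depend on the unstated rounding rule.

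**5. MMS entry limits of 4 and 8**

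- Upper: RBS must be 1 or 2, so the maximum is 3 + 2 + 3 = 8. The limit cannot be exceeded.
- Lower: a true SFS of 3 recorded as 2 still gives at least 2 + 1 + 1 = 4 under the Section 8.1 minima. Section 10.2 as printed asks for endoscopy above 1, which gives more.
- Averaging leaves a corner case. Under Section 8.1, baseline days (1,2,3) with RBS 1 and endoscopy 1 give 2.00 + 1 + 1 = 4.00, against 3.67 if the last day is ticked too low.

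**6. Bleeding**

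No blood and blood alone correspond at both ends, so RBS 0 and 3 map cleanly. Traces in most stools, or a lot of blood in a minority of stools, have no clear place between RBS 1 and 2. If one day is affected, days (1,1,2) against (1,1,1) average 1.33 against 1.00, which crosses RBS of 1 or less if unrounded.

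**The case against.** The boxes are plainly meant as scores 0 to 3 in order, and a subject with 5 extra stools may well choose the top box, which is the correct score. A reader might infer that such a day must be scored too low; the documents do not support that. A reader might also infer a full point lost for each such day, but the averaging in Section 13.6 cuts it to a third of a point.

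Nor are the MMS entry limits of 4 and 8 generally at risk. With RBS restricted to 1 or 2, a whole-point SFS error cannot cross either limit, and only mixed days at the lower margin can be nudged across. All of this stands.

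The bleeding objection also stands in large part. Appendix C combines appearance with share of time, so it is wrong to say that the scale grades time and the diary grades amount. Because the footnote scores the worst bleeding of the day, a daily severity grade is a reasonable lay version. Pasting the share-of-time wording into a daily box could fit that footnote less well.

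Finally, the e-diary screens are not shown, and Section 13.1 leaves detail to a separate SAP, so a conversion could exist elsewhere. What remains is that Section 9.7.1 and Appendix A carry the same gap and the document states no rule to close it.

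**Conclusion.** The stool-frequency wording is wrong as written: one count that the scale scores as 3 has no diary box and can be recorded as 2 or 3. The effect on the visit SFS is 0.33 per affected day, reaching 1.00 only if all three averaged days are affected. It matters for baseline MMS, MMS change and subjects close to the clinical-response threshold. It reaches remission only through averages of mixed days.

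The documents do not say how often days with exactly 5 extra stools occur, so no effect on response rates or power can be computed. A reader might infer a biased primary result. The documents do not support that: all arms use the same diary under blinding, so the error should be similar across arms and act as noise.

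On bleeding, the finding is limited to a missing statement of how the two middle boxes become RBS 1 and 2. These conclusions rest on the boxes being scored in order and on baseline being averaged like the other visits.

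**What to change.** Reword the last stool box in Section 9.7.1, Appendix A and the e-diary so that it starts at 5: 5 or more times a day more than usual. The cost is a diary text change and its translations. If the diary is already in use, record the version date so that entries made under each wording can be told apart; a later scoring rule cannot recover the count behind a ticked box.

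For bleeding, keep the daily grades and state in the SAP, before unblinding, how the traces and a-lot boxes map to RBS 1 and 2. State in the same place whether the 3-day averages are rounded. Both are short text additions.

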9.7.2 Endoscopy

The screening endoscopy may consist of either a flexible rectosigmoidoscopy or a colonoscopy. A colonoscopy is required during the Screening Phase only for those subjects who have not had a colonoscopy within 12 months prior to the Screening Visit. Subsequent endoscopies (rectosigmoidoscopies) will be performed at Week 8 or at the Early Termination Visit. The flexible rectosigmoidoscopy will not be repeated within 4 weeks of the previous rectosigmoidoscopy.

Images/Videos of all endoscopic procedures (flexible rectosigmoidoscopy/colonoscopy) will be captured and sent to a centralized reader for their assessment, which will be used for the calculation of the MMS. The endoscopy assessment performed by the Investigator will be used

to calculate the MMS for the determination of subjects who do not achieve at least a 20% decrease from baseline in the MMS at Week 8.

Mucosal biopsies, collected for assessment of histological disease activity (Section 9.8), will be performed during the Screening Phase and at the Week 8 Visit when the endoscopies are done. Biopsies should be taken from the most inflamed area of the rectum or rectosigmoid junction, while avoiding ulcerated mucosa. Week 8 biopsies should be taken from the same location as the baseline biopsy. Subjects who discontinue study prior to the Week 8 Visit will have the biopsies performed at the Early Termination Visit with the endoscopy.

Central reading of endoscopies will be performed throughout this study, and a detailed charter will address the standardization of endoscopic procedures, video recordings, and equipment, as well as the criteria for endoscopic assessment. For each subject, video recording of the entire endoscopic procedure will be performed. Annotation of the rectum, sigmoid and descending colon will be performed by the site endoscopist on withdrawal, using the equipment provided.

All video recordings will be quality checked by the central read vendor to produce a video clip visualized up to the splenic flexure only (rectum, sigmoid, and descending colon). The video clips will be read centrally for mucosal lesions and endoscopic severity by an independent gastroenterologist experienced in IBD who is blind to the subject's clinical activity and treatment allocation. The Mayo Clinic Score (MCS) endoscopic sub-score is to be determined both locally (at the investigator site) and centrally as described above. Each segment of the colon up to the splenic flexure (rectum, sigmoid, and descending colon) will be assigned an endoscopic sub-score, and the score from the worst affected segment up to the splenic flexure is to be used for the MCS calculation. In the event that there is a discrepancy between the endoscopic sub-score obtained by the local versus the central readers, a third adjudication read is to be conducted by a different central reader.

Training of the site and central readers, and the adjudication process in the event of a discrepancy between site and central reader; will be described in detail in the Endoscopy charter

9.7.3 Modified Mayo Score

The Mayo Score is an instrument designed to measure disease activity of UC. The Mayo Score ranges from 0 to 12 points. It consists of 4 sub-scores, each graded from 0 to 3 with higher scores indicating more severe disease (Appendix C).

A modification to the Total Mayo Score (TMS) will be implemented in this study. This MMS will be based on the stool frequency, rectal bleeding, and endoscopy sub-scores of the TMS and will exclude the Physician's Global Assessment (PGA) sub-score, since this is a global measure that is subjective in nature. The MMS ranges from 0 to 9 points. Clinical response is defined as a decrease from baseline in modified Mayo Score of at least 2 points and at least 25%, with an accompanying decrease in the RBS of at least 1 point or an absolute RBS of 0 or 1. Clinical remission is defined as an MMS of 2 points or lower, with no individual sub-score exceeding 1 point.

SFS

- RBS
- Endoscopy Sub-score

The frequency of the TMS assessment is described in Table 1 Schedule of Events.

9.7.4 Physician Global Assessment

The PGA is done as part of the Mayo score. It acknowledges 3 other criteria: the subject's daily recollection of abdominal discomfort and general sense of well-being, and other observations, such as physical findings and the subject's performance status.

9.8 Pharmacodynamic/Biological Markers

Peripheral blood will be analyzed for CRP, which is a protein that provides an objective criterion of inflammatory activity. C-reactive protein enables identification of subjects with UC symptoms who have objective evidence of active inflammatory disease (Sands 2015). Fecal calprotectin, a biomarker of intraluminal intestinal inflammation, will be assessed by a central reader. Fecal calprotectin is a directly proportional measurement of neutrophil migration to the gastrointestinal (GI) tract. The schedule and frequency of PD/biological markers are discussed in Table 1 Schedule of Events.

Intestinal mucosal biopsies will be performed during endoscopy as indicated in Table 1 Schedule of Events in order to assess inflammatory cell infiltration and tissue destruction in the colonic mucosa. One biopsy will be stained with Haematoxylin Eosin (H&E), and the degree of cellular inflammatory infiltrate and of tissue destruction present in the colonic mucosa will be measured using a microscopic tissue grading score.

9.9 Pharmacokinetics

A PK sub-study will be conducted at selected sites to evaluate the PK profile of GED-0507-34-Levo (parent compound) and N-Acetyl-GED-0507-34-Levo (metabolite) in subjects with active UC and to explore the relationship between GED-0507-34-Levo PK exposures and key efficacy endpoints. The target for the PK sub-study is to achieve participation of approximately 50% of the randomized subjects. A separate consent will be signed for this assessment at the Screening Visit.

Pharmacokinetic measurements will be carried out by Accelera Srl ([name]) using a validated method for the detection of GED-0507-34-Levo and its metabolite N-Acetyl-GED-0507-34-Levo in Human Plasma by liquid chromatography – tandem mass spectroscopy (LC-MS/MS).

9.9.1 Pharmacokinetics Blood Draw

For each subject participating in the PK sub-study, the date and time of his/her first dose will be recorded in the source documents and eCRF.

The subjects participating in the PK sub-study will have 4 blood specimens drawn (1 predose during the treatment and 3 postdose). For the predose blood draw, the subject must be reminded to provide the date and time of his/her last evening dose from the day before the visit, which will be recorded in the source documents and eCRF together with the blood draws prior to the morning intake of the compound.

Postdose plasma population PK samples should be taken at a random time between 2 to 4 hours postdose, > 4 to 6 hours postdose, and > 6 to 10 hours postdose. The date and time of his/her dose prior to the blood draws and the date and time of blood draws will be recorded in the source documents and eCRF.

PK blood draws are to take place in the clinic at Visits 4 (Week 2), 5 (Week 4), 6 (Week 6), and 7 (Week 8). It is recommended that subjects have 1 blood specimen collected from each of these time windows over the course of the PK sub-study.

Specific details regarding collection, handling, processing, storage, and shipment of PK samples will be presented separately.

9.10 Dosing

9.10.1 Investigational Product Dispensing and Counting

After the subject has satisfied all inclusion and exclusion criteria, IP will be dispensed as specified by the IWRS. Subjects must be instructed to return all previously issued empty HDPE bottles and/or unused IP at the time that new IP is issued. A detailed record of tablets issued and returned at each visit must be maintained in the subject's record.

9.11 Early Termination Visit

The Early Termination Visit is based on the subject's withdrawal from the study prior to Week 8. Participation in the study is completely voluntary. Subjects are also free to withdraw from the study at any time if they feel they are not benefiting from the study in order to receive rescue therapy and/or receive treatment with standard medical care. In addition, the Investigator may discontinue the subject from the study at any time based on his/her assessment of clinical efficacy and/or safety. The decision to discontinue a subject remains the responsibility of the treating physician, which will not be delayed or refused by the sponsor. When a subject withdraws or is discontinued from the study, every effort should be made to complete as many safety and efficacy assessments as reasonably appropriate. Refer to Table 1 for the assessments to be performed at the Early Termination Visit.

9.11.1 Lost to Follow-up

Subjects will be considered lost to follow-up when they fail to attend study visits without stating an intention to withdraw from the study. The Investigator should show due diligence by documenting in the source documents the steps taken to contact the subject through at least 2 telephone calls and/or emails and 1 registered letter. After all reasonable attempts have been made to contact the subject, the subject should be recorded as "lost to follow-up" in the eCRF.

9.12 Study Completion

The End of Trial is defined as either the date of the last visit of the last subject to complete the study or the date of receipt of the last data point from the last subject that is required for primary, secondary, and/or exploratory analysis, as pre-specified in the protocol and/or the SAP, whichever is the later date.

Study completion for an individual subject is defined as reaching the Week 9 Follow-up Visit. Subjects not meeting this definition will be considered early termination subjects.

10 STUDY POPULATION

10.1 Number of Subjects and Sites

Approximately 207 subjects will be enrolled in this study at approximately 85 sites.

10.2 Inclusion Criteria

Subjects must satisfy the following criteria to be enrolled in the study:

- 1. Male or female aged 18 and over at the time of signing the informed consent.
- 2. Must understand and voluntarily sign an ICF prior to any study-related assessments/procedures being conducted.
- 3. Must be able to adhere to the study visit schedule and other protocol requirements.
- 4. Diagnosis of UC with a duration of at least 3 months prior to the Screening Visit.
- 5. MMS ≥ 4 to ≤ 8 (range: 0 9) prior to randomization in the study
 - SFS > 1 and RBS = 1 or 2
 - Mayo endoscopic sub-score > 1 and < 3 prior to randomization in the study
- 6. Subjects are required to have a colonoscopy if one has not been performed within 12 months prior to the Screening Visit.
- 7. Subjects who have relapsed on maintenance therapy with doses of 5-ASA \leq 2.4 g/day.
- 8. Must meet the following laboratory criteria:
 - WBC count $\ge 3000/\text{mm}^3$ ($\ge 3.0 \times 10^9/\text{L}$) and $< 14,000/\text{mm}^3$ ($< 14 \times 10^9/\text{L}$)
 - Platelet count $\ge 100,000/\text{mm}^3 \ (\ge 100 \times 10^9/\text{L})$
 - Serum creatinine $\leq 1.5 \text{ mg/dL}$ ($\leq 132.6 \mu \text{mol/L}$)
 - AST (SGOT) and ALT (SGPT) ≤ 2 upper limit of normal (ULN). If initial test shows ALT or AST > 2 ULN, 1 repeat test is allowed during the screening period
 - Total bilirubin ≤ 2 mg/dL (≤ 34 mol/L) and albumin > lower limit of normal (LLN). If initial albumin test result is < 2 g/dL, 1 repeat test is allowed during the screening period
 - Hemoglobin $\geq 9 \text{ g/dL}$ ($\geq 5.6 \text{ mmol/L}$)
- 9. FCBP must have a negative pregnancy test at screening and the Baseline Visit. While on IP and for at least 28 days after taking the last dose of IP, FCBP who engage in activity in which conception is possible must use one of the approved contraceptive options² described below:

Option 1: Any one of the following highly effective methods: hormonal contraception (oral, injection, implant, transdermal patch, vaginal ring); intrauterine device (IUD); tubal ligation; or partner's vasectomy

OR

- **Option 2:** Male or female condom (latex condom or nonlatex condom NOT made out of natural [animal] membrane [for example, polyurethane]); PLUS one additional barrier method: (a) diaphragm with spermicide; (b) cervical cap with spermicide; or (c) contraceptive sponge with spermicide
- 10. Male subjects (including those who have had a vasectomy) who engage in activity in which conception is possible must use barrier contraception (male latex condom or nonlatex condom NOT made out of natural [animal] membrane [for example, polyurethane]) while on investigational product and for at least 28 days after the last dose of investigational product.

10.3 Exclusion Criteria

The presence of any of the following will exclude a subject from enrollment:

- 1. Diagnosis of Crohn's disease, indeterminate colitis, ischemic colitis, microscopic colitis, radiation colitis, or diverticular disease-associated colitis.
- 2. UC restricted to the distal 15 cm or less (eg, ulcerative proctitis).
- 3. Subjects who have had surgery as a treatment for UC or who, in the opinion of the Investigator, are likely to require surgery for UC during the study.
- 4. Clinical signs suggestive of fulminant colitis or toxic megacolon.
- 5. Evidence of pathogenic enteric infection.
- 6. History of colorectal cancer or colorectal dysplasia.
- 7. Prior use of any TNF inhibitor (or any biologic agent).
- 8. Prior use of mycophenolic acid, tacrolimus, sirolimus, cyclosporine, or thalidomide.
- 9. Subjects who have relapsed on maintenance therapy with doses of 5-ASA > 2.4 g/day will be excluded from the study. If a subject had a recent 5-ASA dose reduction from > 2.4g/day to ≤ 2.4 g/day and relapsed within 2 weeks of that dose reduction.
- 10. Oral aminosalicylates are not permitted during the study.
- 11. Use of budesonide-MMx within the last 8 weeks.
- 12. Use of oral and/or IV corticosteroids within 2 weeks of the Screening Visit.
- 13. Use of immunosuppressants (azathioprene [AZA], 6-mercaptopurine [6-MP] or methotrexate [MTX]) within 8 weeks of the Screening Visit.
- 14. Use of topical treatment with 5-ASA or corticosteroid enemas or suppositories within 2 weeks of the Screening Visit.
- 15. History of any clinically significant neurological, renal, hepatic, GI, pulmonary, metabolic, cardiovascular, psychiatric, endocrine, hematological disorder or disease or any other medical condition that, in the Investigator's opinion, would preclude participation in the study.

- 16. Prior history of suicide attempt at any time in the subject's lifetime prior to randomization in the study or major psychiatric illness requiring hospitalization within 3 years of study randomization.
- 17. Any condition, including the presence of laboratory abnormalities, which places the subject at unacceptable risk if he/she was to participate in the study or confounds the ability to interpret data from the study.
- 18. Pregnant or breast feeding.
- 19. History of any of the following cardiac conditions within 6 months of screening: myocardial infarction, acute coronary syndrome, unstable angina, new onset atrial fibrillation, new onset atrial flutter, second- or third-degree atrioventricular block, ventricular fibrillation, ventricular tachycardia, heart failure, cardiac surgery, interventional cardiac catheterization (with or without a stent placement), interventional electrophysiology procedure, or presence of implanted defibrillator.
- 20. Known active current or history of recurrent bacterial, viral, fungal, mycobacterial, or other infections (including but not limited to tuberculosis, atypical mycobacterial disease, and herpes zoster), human immunodeficiency virus (HIV), or any major episode of infection requiring hospitalization or treatment with IV or oral antibiotics within 4 weeks of screening.
- 21. Subjects with active hepatitis B infection, as described in Appendix D, are ineligible for the study. Subjects without current hepatitis B infection, as described in Appendix E, may participate in the study.
- 22. Subjects who are positive for the hepatitis C antibody are not eligible for the study.
- 23. History of congenital or acquired immunodeficiency (eg, Common Variable Immunodeficiency Disease).
- 24. History of malignancy, except for:
 - a. Treated (ie, cured) basal cell or squamous cell in situ skin carcinomas
 - b. Treated (ie, cured) cervical intraepithelial neoplasia (CIN) or carcinoma in situ of the cervix with no evidence of recurrence within the previous 5 years
- 25. Any condition that could affect oral drug absorption, including gastric resections, gastroparesis, or bariatric surgery, such as gastric bypass.
- 26. Subjects who have received any investigational drug or device within 3 months of study randomization.
- 27. History of alcohol, drug, or chemical abuse within the 6 months prior to screening.
- 28. Known hypersensitivity to GED-0507-34-Levo or any excipients in the formulation.

